EFFECTIVENESS OF INDIVIDUALIZED
DIETARY COUNSELING AND
NUTRITIONAL MONITORING IN
REDUCING CANCER-ASSOCIATED
CACHEXIA AMONG FEMALE BREAST
CANCER PATIENTS

Submitted by

[name] and [name]

07 February 2024

Effectiveness of Individualized Dietary Counseling and Nutritional Monitoring in Reducing Cancer-Associated Cachexia among Female Breast Cancer Patients

INTRODUCTION

Background of the Study

Cancer-associated cachexia (CACS) is a multifactorial syndrome marked by involuntary weight loss, muscle wasting, systemic inflammation, and metabolic abnormalities. Among patients with advanced-stage breast cancer, CACS significantly impacts quality of life, treatment tolerance, and survival. In low- and middle-income countries like Pakistan, cachexia often remains underdiagnosed and poorly managed due to limited supportive care resources. This study aims to assess the effectiveness of personalized dietary counseling and regular nutritional monitoring in reducing cachexia severity using the validated Mini-CASCO tool.

Objectives of the Study

Primary Objective:

- To evaluate whether individualized dietary counseling combined with monthly nutritional monitoring reduces cachexia severity over six months in female patients with advanced breast cancer.

Secondary Objectives:

- To assess changes in body composition, appetite, physical performance, inflammatory markers, and quality of life.
- To determine the adherence and feasibility of implementing nutrition-sensitive supportive care in an oncology setting.

METHODOLOGY

Study Design

This is a two-arm; parallel-group, randomized controlled trial (RCT) conducted over a six-month intervention period at Fauji Foundation Hospital, Rawalpindi, Pakistan. Participants will be randomly assigned (1:1) to receive either standard oncological care alone (control group) or standard care plus tailored nutritional counseling and monthly monitoring (intervention group). Randomization will be block-stratified with allocation concealment using opaque, sealed envelopes.

Patient Selection and Enrollment

Inclusion Criteria:

- Female patients aged 20–60 years.
- Histologically confirmed advanced-stage breast cancer.
- $\geq 5\%$ unintentional weight loss in the previous 6 months.
- Hemoglobin < 12 g/dL or energy intake < 1500 kcal/day.

Exclusion Criteria:

- Concurrent non-cancer-related malnutrition.
- Pregnancy or lactation.
- GI/endocrine disorders affecting nutrition.
- Enrollment involved screening for eligibility, obtaining informed consent, and randomization using sealed, opaque envelopes.

Baseline data were collected before group assignment.

Eligible patients will undergo informed consent. Those consenting will be randomized using a block randomization method. Baseline data will be collected prior to group assignment.

Intervention

Intervention Group:

- Individualized dietary counseling based on baseline nutritional status
- Monthly monitoring (every 15–21 days) of weight, intake, and biochemical parameters
- Light physical activity guidance and psychosocial support
- Dietary goals: 25–30 kcal/kg/day and 1.2–1.5 g/kg/day protein
- Compliance tracked through food intake records and goal adherence checklists

Control Group:

Standard oncological care without structured nutritional intervention

Ethical Considerations

This study will be approved by the Ethical Review Board of Fauji Foundation Hospital, Rawalpindi. All participants will provide written informed consent prior to enrollment. The study adheres to the ethical principles outlined in the Declaration of Helsinki. Confidentiality will be ensured through unique patient identifiers and restricted data access.

Protocol Amendments

No protocol amendments have been made to date. Any future amendments will be reviewed and approved by the Ethical Review Board and documented accordingly in the PRS system.

REFERENCES

4. World Health Organization. *Global Breast Cancer Initiative Implementation Framework: Saving Lives, Improving Quality of Care.* Geneva: World Health Organization; 2021. Available from: <https://www.who.int/publications/i/item/9789240022616>

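### The intervention arm also receives activity guidance and psychosocial support, so unless standard care already supplied both, a between-arm difference supports a claim about a four-part package, not about counselling plus monitoring alone

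*Protocol*

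**What the plan says.** The protocol's Study Design defines the randomised contrast. Control is "standard oncological care alone (control group" and the other arm is "standard care plus tailored nutritional counseling and monthly monitoring (intervention group". The primary objective has the same content: "To evaluate whether individualized dietary counseling combined with monthly nutritional monitoring reduces cachexia severity over six months". The Background aim refers to "personalized dietary counseling and regular nutritional monitoring in reducing cachexia severity". The protocol title, SAP title, SAP Introduction and SAP primary objective also name counselling and monitoring and nothing else. The SAP's Study Design section names no component.

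The protocol's Intervention section is broader. Besides counselling and monitoring, the intervention arm is given "Light physical activity guidance and psychosocial support". The control entry reads "Standard oncological care without structured nutritional intervention" and mentions neither addition.

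The same section sets dietary goals for energy and protein, and follows compliance with food records and checklists of goal adherence. Its monitoring entry reads "Monthly monitoring (every 15–21 days) of weight, intake, and biochemical parameters". The protocol's secondary objective on adherence and feasibility uses a wider label for supportive care that takes account of nutrition, but it names neither activity guidance nor psychosocial support.

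**The concern.** Study Design and the Intervention section of the same protocol disagree about what separates the arms. If the primary objective is answered as worded, any difference in Mini-CASCO will be read as the effect of counselling plus monitoring, although that arm received two further components. A hospital acting on that reading could adopt counselling and monitoring and leave out half of what was delivered.

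The issue also reaches the secondary objectives, which include "To assess changes in body composition, appetite, physical performance, inflammatory markers, and quality of life". Activity guidance could plausibly affect physical performance, and psychosocial support could plausibly affect quality of life. That is an assumption: the documents give no size for either effect, and none is claimed here for Mini-CASCO.

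**Working it through.** **What is named where.** The Intervention section lists four components: (1) individualised dietary counselling, (2) monitoring, (3) light activity guidance, (4) psychosocial support. The dietary goals and compliance tracking are taken as part of counselling.

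| Place | Components named |
|---|---|
| Protocol title | 1, 2 |
| Protocol, Background aim | 1, 2 |
| Protocol, primary objective | 1, 2 |
| Protocol, Study Design | 1, 2 |
| SAP title | 1, 2 |
| SAP, Introduction | 1, 2 |
| SAP, primary objective | 1, 2 |
| Protocol, Intervention | 1, 2, 3, 4 |

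Components 3 and 4 appear in none of the first seven rows. Those rows largely repeat one another, so the count shows that the wording is consistent. It does not measure impact.

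**What two arms can identify.** Let D be the between-arm difference. Let N be the part due to counselling and monitoring, and X the part due to activity guidance and psychosocial support, including any interaction with N. Then D = N + X. The trial estimates D only, and any split with N = D − X fits the data equally well. No analysis in the SAP's Outcome Measures Table separates the two.

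If standard care supplied components 3 and 4 equally to both arms, X = 0 and D = N. If it did not, D belongs to the package. The documents do not say which holds, but they list these components under the intervention arm only.

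**Sample size.** The SAP gives d = 0.5, power 80%, alpha 0.05 and 64 per group. A two-sided two-sample t-test with those inputs needs 63.77 per group, rounded up to 64, so the figure reproduces. The SAP does not state sidedness; two-sided is assumed. The calculation sizes whatever contrast is randomised, that is D, so naming the package does not change it.

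**Monitoring interval.** Six months is taken as 182 days, counting occasions after baseline.
- Monthly: 182 / 30.4 = 5.99, about 6. With a 28-day month, 182 / 28 = 6.5, so 6 whole occasions.
- Every 21 days: 182 / 21 = 8.67. The 8th falls on day 168 and the 9th on day 189, outside the window, so 8 whole occasions.
- Every 15 days: 182 / 15 = 12.13. The 12th falls on day 180, so 12 whole occasions.

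The contrast is about 6 against 8 to 12, or 8 / 6 = 1.33 to 12 / 6 = 2.0 times as many.

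**The case against.** The strongest reply is that this is labelling. The extra components are disclosed in the section that defines the arm, multicomponent interventions are legitimate, and titles often name only the lead elements. An objective is not a conclusion, and neither document contains a rule for wording one. It is true that the design is sound and that misattribution is a risk rather than something already done. But Study Design does more than label: it defines the contrast, and it disagrees with the Intervention section. The primary objective is the question the report will be expected to answer.

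A second reply is that standard care, which both arms receive, may already include activity advice and psychosocial support, since the control entry excludes only structured nutritional intervention. This stands as a condition on the point. It is the less likely reading, because the protocol lists the two elements for one arm only.

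A third is that the feasibility objective's wider label could cover the package. It names neither element and concerns adherence and feasibility, so it softens the contrast without removing it.

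Some readers might go further in ways the documents do not support:
- **That delivery of the extra components went unmeasured.** No activity or psychosocial goal is stated, but the content of the adherence checklists is unspecified and the SAP's adherence row is not limited to diet.
- **That the monitoring schedule cannot be known.** The 15–21 days stand in parentheses in the section that defines delivery. The natural reading is that they govern and that 'monthly' is loose wording.

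**Conclusion.** The point holds in conditional form. Provided standard care did not already supply activity guidance and psychosocial support to both arms, the trial can support a conclusion about standard care plus a four-part package against standard care alone. It cannot support one about counselling plus monitoring by themselves. Two of four components are affected, and their share of any effect cannot be estimated from this design.

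A reader might infer that the comparison is biased or underpowered. The documents do not support that: package against standard care is a proper randomised contrast and the sample size reproduces. What fails is the match between the stated question and what was randomised. This should be corrected because it changes what the trial can be said to show.

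The interval conflict is a minor wording matter. It affects how well the schedule can be reproduced and implies no bias in any outcome.

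**What to change.** Issue a dated clarification, approved by the Ethical Review Board and recorded in the PRS system as the Protocol Amendments section requires, with the protocol and SAP text of 07 February 2024 left visible. Carry the same text into the report. It should:

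- state the primary comparison and conclusion as standard care plus the four-part package (dietary counselling, monitoring, light activity guidance, psychosocial support) against standard care alone;
- state that component effects cannot be separated;
- describe what standard care included for activity advice and psychosocial support;
- treat 15–21 days as the operative monitoring interval, drop 'monthly', and report the interval actually delivered.

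The SAP's sample size section already reports 134 randomised and 130 completed, so this governs interpretation and reporting rather than conduct. The cost is one approval, one registry entry and a less specific claim for dietary counselling. No test changes and no new data are needed. Delivery of the extra components, and contact counts, can be reported only if they were recorded.

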Statistical Analysis Plan (SAP)

Effectiveness of Individualized Dietary
Counseling and Nutritional
Monitoring in Reducing Cancer-
Associated Cachexia among Female
Breast Cancer Patients: A
Randomized Controlled Trial

07 February, 2024

Introduction

This SAP outlines the pre-specified statistical methodology used to evaluate the effectiveness of individualized dietary counseling combined with regular nutritional monitoring in reducing cancer-associated cachexia among female breast cancer patients. The protocol adheres to the CONSORT guidelines.

Objectives

Primary Objective:

To assess the effect of individualized dietary counseling and regular nutritional monitoring on cachexia severity using the Mini-CASCO tool after six months.

Secondary Objectives:

To evaluate changes in:

- Body composition
- Inflammatory and metabolic markers
- Physical performance
- Appetite levels
- Quality of life (QoL)

Study Design

- **Design:** Prospective, parallel-arm, randomized controlled trial
- **Randomization:** 1:1 ratio with block-stratified randomization (block size = 4)
- **Blinding:** Outcome assessors and statisticians were blinded

Sample Size Determination

Using G*Power for repeated-measures ANCOVA:

- Effect size (Cohen's d): 0.5
- Power: 80%
- Alpha: 0.05
- Estimated N: 64 per group (total 128)
- Final enrollment: 134 randomized; 130 completed (65 per group)

Handling of Missing Data

- Missing data (<5%) addressed via Multiple Imputation (Chained Equations, 10 iterations)
Assumed Missing At Random (MAR)
Sensitivity analyses compared results with and without imputation

Effect Size Estimations

- Cohen's d: within-group effect size
- Partial eta squared (η^2): between-group comparisons
- Interpretation thresholds:
 - $d \geq 0.8$ = large
 - $\eta^2 \geq 0.14$ = large

Software

- Statistical analyses were performed using IBM SPSS Statistics v25.0
- Graphs and tables created using Excel and SPSS

Validation and Sensitivity Analyses

Key assumptions for ANCOVA validated:

- Normality via Shapiro-Wilk test
- Homogeneity of variance via Levene's test
- Sphericity via Mauchly's test
- Sensitivity analysis excluding imputed data showed similar trends

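### A fixed block size of 4, at one hospital with arms that staff can tell apart, could let up to about one third of allocations be deduced, and no safeguard beyond sealed envelopes is described

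*SAP*

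**What the plan says.** The SAP, under Study Design, gives "1:1 ratio with block-stratified randomization (block size = 4" and names no other size. The protocol, under Study Design, says "Randomization will be block-stratified with allocation concealment using opaque, sealed envelopes". Its Patient Selection and Enrollment section adds "Those consenting will be randomized using a block randomization method" but gives no block size.

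Three other statements bear on the point:

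- **Site.** The trial is "conducted over a six-month intervention period at Fauji Foundation Hospital, Rawalpindi, Pakistan", so one set of staff may see every assignment.
- **Blinding.** The SAP states "Outcome assessors and statisticians were blinded". Recruiting and treating staff are not listed. The control arm is "Standard oncological care without structured nutritional intervention", and no sham or attention control is described.
- **Baseline.** The protocol says "Baseline data will be collected prior to group assignment". In the SAP's Outcome Measures Table (Appendix A), the baseline score is the only covariate for the primary outcome.

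Neither document gives the stratification factors, who prepares the sequence, who holds and opens the envelopes, whether these are sequentially numbered, or whether the block size is kept from recruiters.

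**The concern.** Opaque envelopes stop anyone from reading the next allocation. They do not stop anyone from working it out. In a block of 4 at 1:1, the fourth allocation follows from the first three, and the third follows from the first two whenever those match. Past assignments are visible here because one group receives repeated counselling and the other does not.

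A recruiter with that foreknowledge can approach, defer or pass over a patient according to the coming arm. Eligibility leaves some room for this, since recent weight loss and daily energy intake both involve judgement and timing. Taking baseline data before assignment protects the measurements, but not the decision whom to enrol or when. Adjusting for baseline Mini-CASCO removes only the selection that this score carries.

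**Working it through.** **Inputs.** From the SAP: block size 4, 1:1 ratio, 134 randomised, d = 0.5, alpha 0.05, power 80%, 64 per group. Assumed: 67 per arm (134/2), one stratum unless stated, and the selection effect g.

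**The plan's own figure.** The documents give no predictability figure. Their sample size reproduces: a two-sided two-sample t-test at d = 0.5 needs 64 per group (power 0.801). The values d = 0.5 and 80% power are therefore usable yardsticks.

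**Forced allocations.** A block has 6 equally likely orders. The chance that an allocation is forced by the earlier ones is 0, 0, 1/3 and 1 at positions 1 to 4.

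- Per block: 1/3 + 1 = 4/3, and (4/3)/4 = 33.3%.
- For 134 patients: 33 full blocks plus 2 patients, so 33 × 4/3 = 44, and 44/134 = 32.8%.
- With several strata, incomplete blocks lower this to 32.1% (4 strata), 30.9% (8) and 29.6% (12). The number of strata is an assumption.

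**Best guess.** The chance of a correct guess is 1/2, 2/3, 2/3 and 1 at the four positions, and (0.5 + 0.667 + 0.667 + 1)/4 = 70.8%.

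**Bias.** Suppose staff act only on certain allocations, and shift the expected outcome by +g SD when one arm is coming and by −g SD when the other is. With about one third of each arm affected, the difference in means is g/3 − (−g/3) = 2g/3. Using 44/134, it is 2 × 0.328 × g. The standard error is √(2/67) = 0.173. Type I error is two-sided and unadjusted.

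| Assumed g | Bias (SD) | Type I error, formula | Type I error, simulation |
|---|---|---|---|
| 0.1 | 0.07 | 6.7% | about 7% |
| 0.25 | 0.16 | 16% | about 15% |
| 0.5 | 0.33 | 48–49% | about 44–45% |

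The simulated rate is lower at g = 0.5 because the shifts also inflate the within-arm variance.

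**Varying the block size.** Take an observer who knows the possible sizes but not their order.

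| Blocks | Certain | Best guess correct |
|---|---|---|
| 4 only | 33% | 71% |
| 4 and 6 | 5.5% | 69% |
| 4, 6 and 8 | 2.3% | 68% |

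**Adjusting for allocation probability.** Let P be the probability of the intervention given earlier assignments in the stratum, and T the arm. Because E(T given P) = P, the part of T left after P is unrelated to any selection that depends on P. Including P therefore removes such bias. In simulation it brought bias to about zero and type I error to about 5% at every g above.

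The price is collinearity. Var(P) by position is 0, 1/36, 1/12 and 1/4, with mean 13/144. Dividing by Var(T) = 1/4 gives 0.36. The variance of the treatment effect rises by 1/(1 − 0.36) = 1.57. By normal approximation, power at d = 0.5 goes from Φ(0.5/0.173 − 1.96) = 82% to Φ(0.5/(0.173 × √1.57) − 1.96) = 64%. Simulations gave 81–82% falling to 62–64%.

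**The case against.** A reader might infer that one third of the allocations were known in advance, and so that the trial lacks the concealment it claims. The documents do not support that. An allocation is certain only to someone who knows or infers the block size, knows the stratum and has followed every earlier assignment in it. No passage says that staff did so, and the protocol leaves the block size out. Sealed envelopes are a genuine mechanism, which predictability weakens without making it absent. That the trial is open-label is likewise a sound inference and not a stated feature.

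Three further objections stand in part:

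- **The larger type I errors are conditional.** They rest on an assumed g, on action at every certain allocation in both directions, and on a model without the baseline score, which is not the planned analysis. The documents support no value of g.
- **New blocks may come too late.** The SAP reports 134 randomised and 130 completed. The protocol of the same date mixes past and future tense, and its future tense does not show that enrolment is still open.
- **Varying the block size helps less than the fall in certain allocations suggests.** Best-guess success drops only from 71% to 68%. What is removed is mostly certainty.

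None of this supplies a safeguard. The size is stated in a plan dated the same day as the protocol, and a recurring two-and-two pattern at one site can be inferred.

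**Conclusion.** The concern holds as a risk of selection at enrolment. Up to about one third of allocations (about 44 of 134 in one stratum, about 30% with 12 strata) could be deduced by staff who know or infer the block size and track assignments. The documents describe nothing beyond the envelopes to prevent it.

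Whether any bias followed cannot be told from the documents. If staff acted on every certain allocation, it would be about 2g/3 SD. That is minor at g = 0.1, but about two thirds of the planned effect at g = 0.5 (0.33/0.5). The enumeration is exact; the bias figures are illustrations over assumed g. The sample size is not affected.

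**What to change.** **In either case,** state the stratification factors, who generated the sequence, who held and opened the envelopes, whether they were sequentially numbered, and who knew the block size.

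**If any enrolment remains,** use permuted blocks of randomly varying size (for example 4, 6 and 8) within strata. Have the list prepared and held by someone not involved in enrolment, and withhold the sizes from recruiters. The cost is a new list and one line of the SAP, with slightly more possible imbalance within strata when blocks are incomplete.

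**If randomisation is complete,** keep the planned primary ANCOVA and add a labelled sensitivity analysis:

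1. Compute each patient's allocation probability from earlier assignments in her stratum, using the actual strata.
2. Test its association with baseline prognostic variables, not with the Mini-CASCO score alone, since the ANCOVA already adjusts for that score.
3. Test its association with the outcome after adjusting for arm and baseline score.
4. Report the treatment effect with the probability as a covariate.

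This needs only the sequence, the strata and data already held. It has two limits. Power at d = 0.5 falls from about 81% to about 62%, so this model must not replace the primary analysis. The probability term is also an insensitive test: in simulation without the baseline score it detected selection in about 24% of trials at g = 0.25 and about 71% at g = 0.5. A non-significant result therefore does not rule selection out.

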Appendix A: List of Variables

Outcome Measures Table

| Outcome | Type | Statistical Test | Covariates | Assumption Checks |
|---|-----------|----------------------------------|-----------------|--|
| Change in total Mini-CASCO score | Primary | Repeated-measures ANCOVA | Baseline score | Normality, sphericity (Mauchly's test) |
| Domain-specific Mini-CASCO changes | Secondary | Repeated-measures ANCOVA | Baseline scores | Same as above |
| Within-group differences | Secondary | Paired t-tests | | Normality |
| Between-group effect size | Secondary | Partial eta squared (η^2) | | |
| Compliance/adherence | Secondary | Frequency, percentage | | |

List of Variables Table

| Variable | Type | Tool/Scale |
|------------------------------|-----------------|--|
| Weight | Continuous | Digital scale |
| Lean body mass | Continuous | Bioelectrical impedance analysis |
| CRP, Albumin, Hb, TLC | Continuous | Blood test |
| ECOG performance | Ordinal | ECOG Scale |
| Appetite | Ordinal | Simplified Nutritional Appetite Questionnaire (SNAQ) |
| QoL | Continuous | EORTC QLQ-C30 (Urdu version) |
| Total Mini-CASCO | Composite score | 0–100 scale |

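### Does the unexplained repeated-measures ANCOVA label on the sample size leave 64 per group or its 80% power in doubt?

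*SAP*

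**What the plan says.** The SAP's Sample Size Determination section opens with "Using G*Power for repeated-measures ANCOVA". The inputs are "Effect size (Cohen's d): 0.5", 80% power and alpha 0.05, and the result is "Estimated N: 64 per group (total 128"). The same section reports 134 randomized and 130 completed, 65 in each group.

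The primary objective in the SAP is an effect on cachexia severity "using the Mini-CASCO tool after six months". In the Outcome Measures Table of Appendix A the primary outcome is "Change in total Mini-CASCO score", analysed by repeated-measures ANCOVA with the baseline score as covariate. The Validation and Sensitivity Analyses section lists "Sphericity via Mauchly's test" among the assumption checks.

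Neither document gives a Mini-CASCO assessment schedule. The only interim schedule is in the Protocol, under Intervention Group: "Monthly monitoring (every 15–21 days) of weight, intake, and biochemical parameters". It does not mention Mini-CASCO. The control arm is described as "Standard oncological care without structured nutritional intervention".

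One further line bears on the meaning of d. The SAP's Effect Size Estimations section assigns Cohen's d to within-group effects and partial eta squared to comparisons between groups.

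**The concern.** A repeated-measures calculation needs more inputs than the SAP lists: the number of occasions, the correlation between them, and whether the group term or the group-by-time term is tested. None is given. Nor is it said whether d = 0.5 is in units of the raw SD, the SD of change, or the SD left after baseline adjustment, and there is no Mini-CASCO SD to convert it into points. The within-group definition of d elsewhere in the SAP adds to the doubt.

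Two things could be at stake. If the label and the number came from different calculations, 64 per group might give less than 80% power for the six-month comparison. And a reader cannot say what Mini-CASCO difference the trial was planned to detect. The planned sphericity check also sits oddly with an outcome for which only baseline and six months are evident.

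**Working it through.** **Inputs from the SAP:** d = 0.5, power 80%, alpha 0.05, 1:1 allocation, 64 per group, 65 completers per group, baseline score as covariate. **Assumed:** two-sided alpha, equal variances at both times, baseline to six-month correlation r = 0.3, 0.5 or 0.7.

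**1. Reproducing 64.** Two-sample t-test, noncentrality d·√(n/2), df 2n − 2:
- n = 63: 79.5%
- n = 64: noncentrality 0.5·√32 = 2.83, power 80.15%
- n = 65: 80.8%

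The smallest n reaching 80% is 64. A one-sided test would need 51, so the SAP's figure is two-sided. An ANCOVA F-test with f = d/2 = 0.25, two groups and one covariate (df 2n − 3 = 125) gives a total of 128 and 80.14%. A comparison of change scores with d in change-SD units is again the two-sample t-test, so it also gives 64.

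**2. Does a multi-occasion calculation return 128?** With f = 0.25, 2 to 7 occasions (m) and r from 0.3 to 0.7:
- group term, noncentrality N·f²·m/(1 + (m − 1)r): total N 54 to 110
- group-by-time term, noncentrality N·f²·m/(1 − r): total N 12 to 46

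None gives 128, and each asks for fewer patients. The stated N matches a comparison of one value per patient between two groups.

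**3. What d = 0.5 means in raw SD units.** Raw basis: 0.5. Change basis: 0.5·√(2(1 − r)). Adjusted basis: 0.5·√(1 − r²).

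| r | raw | change | adjusted | largest ÷ smallest |
|---|---|---|---|---|
| 0.3 | 0.50 | 0.59 | 0.48 | 1.24 |
| 0.5 | 0.50 | 0.50 | 0.43 | 1.15 |
| 0.7 | 0.50 | 0.39 | 0.36 | 1.40 |

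Pooling over all three correlations gives 0.36 to 0.59, a 1.7-fold range, but that mixes the choice of SD with the assumed r. For an assumed Mini-CASCO SD of 10 to 20 points the same extremes become 3.6 to 11.8 points, and the doubling of the assumed SD is the largest part of that spread.

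**4. Power of the baseline-adjusted six-month contrast at 64 per group.** Divide the raw-SD difference by √(1 − r²) and use the noncentral t:

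| r | raw | change | adjusted |
|---|---|---|---|
| 0.3 | 84% | 94% | 80% |
| 0.5 | 90% | 90% | 80% |
| 0.7 | 98% | 86% | 80% |

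On the adjusted scale the effect is 0.5/√(1 − r²), 0.5·√(2/(1 + r)) or 0.5. None falls below 0.5 for r from 0 to below 1, so these bases never give less than 80%.

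**5. The repeated-measures label and Mauchly's test.** With baseline as covariate and one later score, the group effect on the six-month score, on the change, and on the mean of the two occasions has the same t statistic. In 20,000 simulated trials the three agreed to 8 × 10⁻¹⁵. With two occasions there is a single difference between them, so sphericity holds automatically and Mauchly's test can neither fail nor change the result.

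**The case for a change.** The case for amending the SAP is that the omissions are real, are not a product of redaction, and would cost only wording to repair. A reader who follows the stated label does not arrive at 128, and cannot state the planned difference in Mini-CASCO points. All of that stands.

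The reassurance on power also has a limit. If Mini-CASCO were taken at several post-baseline visits and d were in the SD of their average, 64 would again result, yet the six-month contrast would be weaker. Under compound symmetry with 3 or 6 such scores, its baseline-adjusted power is about 57% or 48% at r = 0.3, 75% or 70% at r = 0.5, and 94% or 93% at r = 0.7. The SAP's repeated-measures wording and its sphericity check lean towards more occasions, so this reading cannot be excluded. But no such visits are listed for either arm, and nothing in the SAP expresses d in the SD of an average. It shows that the power claim is secure on the two-occasion readings, not on every conceivable one. It does not show that the SAP's figure is wrong.

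The within-group definition of d does not explain the number either. A paired t-test at d = 0.5 would need 34 patients, not 64 per group. That definition sits in the section on interpreting results and is most naturally read as applying there.

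**Conclusion.** No change to the plan is needed. The missing inputs are a gap in reporting that a statistician fills in the ordinary way: d = 0.5, two-sided alpha 0.05, 80% power and 1:1 allocation give 64 per group for a two-group comparison, and the same total for an ANCOVA with one covariate. Neither 64 nor 80% is shown to be wrong, and the 65 completers per group exceed the target.

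If the occasions are baseline and six months, calling the analysis an ANCOVA of the six-month score and dropping the sphericity check would leave the identical test and the identical result. The one real loss is that the planned difference is uncertain by a factor of 1.15 to 1.40 at a given correlation, which affects how the target is described and not how the trial is analysed.

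This rests on assumed two-sided testing, equal variances, correlations of 0.3 to 0.7, and Mini-CASCO measured only at baseline and six months. The documents state none of these four, though the last is the reading that the listed assessments best support.
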